Specific Aim 2. To examine the efficacy of ICBT for the improvement of opioid dependence and anxiety symptoms relative to Individual Drug Counseling (IDC). We hypothesize that patients will report greater pre-post reductions in interviewer-rated anxiety symptoms and less opioid use in ICBT relative to IDC.

Specific Aim 3. To examine the association between stress reactivity and treatment outcome in opioid-dependent patients. We hypothesize that: (a) higher levels of stress reactivity at baseline will be associated with more days of opioid use following treatment, and (b) reductions in stress reactivity from baseline to post-treatment will be greater in the ICBT group relative to the IDC group.

Specific Aim 4. To examine the association between ovarian sex hormones, negative reinforcement bias, and treatment outcome in opioid-dependent patients. We hypothesize that: (a) greater negative reinforcement bias will be associated with poor treatment outcomes, and that this association will be stronger in women than men, and (b) within women, high progesterone will be associated with lower negative reinforcement bias and less severe opioid symptoms (e.g., opioid craving, anxiety severity).

III. SUBJECT SELECTION

Participants will be recruited for a randomized controlled trial of the efficacy, feasibility, and acceptability of ICBT. We aim to enroll 54 participants in this trial, and anticipate that up to 110 participants will need to complete informed consent and screening in order to initiate treatment. Participants will be recruited via either: (1) invitation to participate by a member of the study staff, or (2) self-selection in response to posted advertisements.

III.1. Inclusion/Exclusion Criteria

Subjects will be **included** if they: (1) are age 18 or older, (2) meet *DSM-5* diagnostic criteria for opioid use disorder, (3) are currently receiving pharmacotherapy for opioid dependence (e.g., buprenorphine, buprenorphine-naloxone, naltrexone, Vivitrol), (4) have used opioids illicitly within the previous 90 days, (5) exhibit clinically-significant anxiety defined as a score of 14 or higher on a clinician-rated anxiety symptom severity scale (the Hamilton Anxiety Rating Scale), (6) meet *DSM-5* diagnostic criteria for a current diagnosis of an anxiety disorder, (7) are able to read and provide informed consent, and (8) intend to remain in the geographical area for the duration of the study period.

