Potentially eligible subjects will be asked to complete the Informed Consent process, at which point the subjects will read through the IRB-approved consent form, and will meet with a research staff member who will answer any questions, explain the schedule of study procedures, and review the risks and benefits of the study. Subjects will be informed about the experimental nature, purpose, risks, and benefits of the study in accordance with procedures of the Partners IRB. There will be no time-limit placed on the consenting process. Research staff members understand that the consent is a process and not simply a matter of signing and dating the consent form. Either the PI or one of the Co-Investigators (serving as designees of the PI) will be available to help explain the study and answer questions. Once the subject consents to participate in the study, the subject will sign and date the consent form along with a member of the research staff. The subject will be provided with a copy of the consent form and the original will be stored in a secure location by a member of the study staff.

Participants will be randomly assigned to receive either ICBT or IDC. This randomization will be stratified by the following variables: (1) presence of a medication for anxiety, (2) gender, (3) type of opioid medication (agonist/partial agonist vs. antagonist), and (4) severity (defined by presence vs. absence of opioid use since initiating pharmacotherapy for opioid use).

V. STUDY PROCEDURES

All participants will receive 12 individual weekly sessions of ICBT or IDC and will complete assessments at baseline, week 12, and 1- and 3-month post-treatment follow-up visits. Breath alcohol screens will be conducted at each session and assessment visit to confirm absence of acute alcohol use. Procedures for response to a positive breathalyzer screen are specified below in Section VII. Qualitative exit interviews will be conducted at the completion of treatment. These interviews will focus on issues related to feasibility and acceptability, such as identifying the most and least helpful sessions and areas for improvement. Details of the procedures are included below.

V.1. Eligibility and Baseline Assessment

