Distress Intolerance Index. The Distress Intolerance Index (DII; McHugh & Otto, 2011) is a 10-item self-report measure of the intolerance of distressing states that was derived from a study of distress intolerance measures. The DII has demonstrated strong internal consistency reliability in clinical and unselected samples (McHugh & Otto, 2011) as well as strong concurrent and discriminant validity and distinguishes clinical from non-clinical groups (McHugh & Otto, 2012).

Drug Use Motives Questionnaire (DUMQ). The DUMQ (Mueser, Nishith, Tracy, DeGirolamo, & Molinaro, 1995) is a 15-item self report inventory designed to provide an assessment of coping, social and enhancement motives for alcohol use (Cooper, Russell, Skinner, & Windle, 1992). We will use a modified DMQ to assess non-alcohol drug use motives (as utilized by Mueser et al., 1995) with the addition of 5 items to assess for use of opioid for pain coping.

Exit Interview. Participants will be asked to complete an exit interview with a study investigator after the completion of the treatment. Participants will be given the opportunity to share feedback on their experience with the treatment and will be asked how well the treatment addressed their needs. This will be audiotaped and transcribed for analysis.

Fagerstrom Test for Nicotine Dependence (FTND). The FTND (Heatherton, Kozlowski, Frecker, & Fagerstrom, 1991) will be used as a continuous measure of nicotine dependence. The FTND has shown good internal consistency, a single dimension factor structure, and positive relationships with degree of nicotine intake as assessed by saliva cotinine. FTND items are combined with other smoking history items in this study.

Hamilton Anxiety Rating Scale (HARS). The HARS (Hamilton, 1959) is an interviewer-administered measure of anxiety symptoms. The Structured Interview Guide for the HARS (Shear et al., 2001) was developed to improve the reliability of the HARS and will be used in this study. This will be the primary outcome measure for the study.

Homework Compliance. Both participants and clinicians will separately rate compliance with homework/skills practice on a weekly basis with a form adapted from an assessment of homework compliance developed by Primakoff, Epstein, & Covi (1986).

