The stress reactivity paradigm includes two imagery conditions (neutral-relaxing, stress related) and a laboratory session. This paradigm will be completed at pre- and post-treatment assessments. During a visit prior to laboratory sessions, participants will complete two Scene Development Questionnaires (Sinha & Tuit, 2012) that are designed to collect information about each imagery condition (a non-drug-related stressful event in their life, and a neutral-relaxing event); scripts for the imagery conditions will be developed using the information collected. Each script will be written, recorded, and edited by trained research staff in order to ensure that scripts are standardized in terms of length and content. During laboratory sessions, participants will listen to each script. The order of the scripts will be randomized. Psychophysiological measures (skin conductance) will be collected before, during, and after each imagery script. Skin conductance response will be collected using a Biopac MP150 system running AcqKnowledge 4.4 software (Biopac Systems Inc., USA) and the Biopac electrodermal activity amplifier (EDA100c). Skin conductance response is used as an index of physiological arousal, and therefore stress reactivity. Subjective measures that will be administered prior to and following each imagery condition include the Positive and Negative Affect Scale (Watson, Clark, & Tellegen, 1988), and the Opioid Craving Scale (Weiss et al., 2003) that has been adapted to assess craving in the present moment (i.e., “right now”). Following each imagery script participants will also be asked to rate how “clearly and vividly” they were able to imagine the scenario on a 10-point visual analog scale.

V.4.4. Urine Toxicology

Participants will provide weekly urine samples to screen for drug use. Although opioid use is the primary outcome for this trial, the presence of other substances of abuse will be used as secondary outcome. We will use the Alere Toxicology iCup 13 panel drug test screening cup, which tests for the presence of the following substances: cocaine, marijuana, opiates, amphetamines, methamphetamines, phencyclidines, benzodiazepines, barbiturates, methadone, tricyclic antidepressants, oxycodone, propoxyphene, and buprenorphine. We will also use a Drug Screen Test Dip Card to test for fentanyl in the urine sample.

V.4.5. Measurement of Sex Hormones and Menstrual Cycle Phase

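### HARS, one of the outcomes called primary, is scored by an interviewer, and nothing in the protocol keeps that interviewer unaware of treatment arm

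*Combined protocol and SAP*

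**What the plan says.** Section V.4.1 calls HARS an "interviewer-administered measure of anxiety symptoms" and adds: "This will be the primary outcome measure for the study". Aim 2 predicts "greater pre-post reductions in interviewer-rated anxiety symptoms" under ICBT, and Section VI models HARS for efficacy. HARS is not the only outcome given that status. Section V.4.4 has the clause "Although opioid use is the primary outcome for this trial", and Table 1 lists HARS, the Timeline Follow-Back and the urine drug screen together under primary outcomes.

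On allocation, Section IV says "Participants will be randomly assigned to receive either ICBT or IDC" and lists the stratification variables. Section V.2 describes the study as an open pilot. Assessments are attributed to research staff in general terms (V.3). Table 1 schedules HARS at screening, post-treatment, and the 1- and 3-month follow-ups.

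The one provision aimed at the quality of the HARS rating is the structured interview guide, which "was developed to improve the reliability of the HARS and will be used in this study". The text contains nothing on masking, an independent evaluator, concealment of arm from assessors, or a check on unmasking.

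**The concern.** HARS needs a judgement by the interviewer. In a comparison of two psychotherapies the participant and the therapist will know what is being delivered, so the interviewer is the person who could be kept unaware. The protocol tests a new treatment under a directional hypothesis. If raters know the arm and score ICBT participants slightly lower, the shift has the same sign as the hypothesised effect, and the analysis cannot tell the two apart.

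The stake is mainly the estimate. Section VI says that this Stage 1 trial is focused on effect sizes and clinically significant change, and that the results would inform power calculations for Stage 2. A rater shift would enter that effect size in full.

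**Working it through.** **1. Do other provisions cover the gap?**

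- *Structured HARS guide (V.4.1):* addresses reliability. A consistent rater who knows the arm can still be consistently shifted.
- *Audiotaping and fidelity review (V.2):* apply to treatment sessions, not to HARS interviews.
- *Staff separation (III.2):* applies when a potential participant already knows the principal investigator. It governs who presents the study, not who rates outcomes.
- *Baseline covariate, random subject effects and intent-to-treat analysis (VI):* a shift that differs by arm and arises after baseline is part of the treatment contrast, so none of these removes it.
- *Primary outcomes collected before stress reactivity (V.3):* helps with ordering, but does not place HARS before the satisfaction form or exit interview, and does not hide the arm.

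**2. Inputs for scale.** From Section VI: N = 54; power at least 0.80; d = .70-.75; repeated-measures correlation r = 0.42 for HARS and below .20 for opioid use; up to 20% loss allowed for. Assumed, because not stated: 1:1 allocation (54/2 = 27 per arm) and two-sided alpha of 0.05. The rater shift b, in SD units, is purely hypothetical.

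**3. The plan's own figure.** With the baseline value as a covariate, minimum d = (1.96 + 0.842) × sqrt(1 − r²) × sqrt(2/27).

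- r = 0.42: 2.802 × 0.9075 × 0.2722 = 0.69
- r = 0.20: 2.802 × 0.9798 × 0.2722 = 0.75

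This reproduces .70-.75 with all 54 analysed, so 27 per arm with a two-sided 5% test is a reasonable reading. Masking would not change this figure.

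**4. Effect of a shift when the true effect is zero.** Without baseline adjustment, SE = sqrt(2/27) = 0.272 and error rate = P(|Z + b/0.272| > 1.96).

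| b (SD) | b/SE | Two-sided error rate |
|---|---|---|
| 0 | 0 | 5% |
| 0.2 | 0.735 | 11.4% |
| 0.3 | 1.102 | 19.7% |
| 0.4 | 1.470 | 31.2% |

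**5. With the planned baseline adjustment.** At r = 0.42 the SE falls to 0.272 × 0.9075 = 0.247, so the same shift counts for more. By the noncentral t, the chance of a significant result in favour of ICBT is 12%, 22% and 36% for b = 0.2, 0.3 and 0.4, against 2.5% with no shift. With 20% loss (27 × 0.8 = 21.6 per arm) and the same adjustment, b = 0.2 gives 10.5%.

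**6. On the effect-size scale.** A shift of 0.3 SD would be 0.3/0.75 = 40% to 0.3/0.70 = 43% of the difference that the trial is powered to detect.

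**The case against.** The strongest reply is that the documents are silent: they do not say that raters know the arm. That stands, and it limits the claim to what could happen under the plan as written.

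A reader might go further and infer that one small team runs the weekly visits, handles the session forms, holds the exit interview and rates HARS, so that every contact discloses the arm. The text does not support this. Team size is not given. For homework, "Both participants and clinicians will separately rate compliance with homework/skills practice on a weekly basis". For the exit interview, "Participants will be asked to complete an exit interview with a study investigator after the completion of the treatment". Self-report forms may be completed electronically, so a HARS rater need not see them, and nothing says that the credibility or key-concepts forms differ by arm. The exit interview, which asks about the most and least helpful sessions, is the contact most likely to reveal the arm; the protocol neither assigns HARS to the person who conducts it nor bars that person from rating.

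A reader might also infer that the whole efficacy question is exposed. It is not. Opioid use is also called primary, and the urine screen is far less open to rater expectation. The point concerns the anxiety half of Aim 2.

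Self-reported anxiety measures (the OASIS and the disorder-specific scale) are free of rater scoring, but participants know their therapy, so these do not settle the matter. For the same reason a masked HARS rater would still be scoring the account of an unmasked participant.

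Finally, the shifts of 0.2 to 0.4 SD have no source in the documents, and a false-positive rate is not the main measure for a trial focused on estimation. Both points stand. The percentages show sensitivity and are not a forecast.

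**Conclusion.** The concern holds for HARS. The plan leaves open an unmasked rating of a subjective outcome called primary, and no other provision closes that gap. An ICBT-IDC difference in HARS, and the effect size taken to Stage 2, could partly reflect rater expectation. It does not follow that raters will be unmasked or that a bias will occur.

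The size is unknown. The figures of about 11%, 20% and 31% rest on the assumed shifts, equal allocation, a two-sided 5% test, no loss and no baseline adjustment. Adjustment makes them somewhat higher; loss to follow-up makes them somewhat lower. This is a cheap improvement worth making. It is not a flaw that invalidates the design.

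**What to change.** State in Section V.4 that:

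- HARS at week 12, 1 month and 3 months is rated by existing research staff who do not treat that participant, do not conduct that participant's exit interview and are not told the arm;
- HARS is done before the satisfaction form and the exit interview;
- participants are asked at the start of the interview not to disclose their treatment;
- any unmasking, and the rater's guess of arm, are recorded.

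Where staffing does not allow this for a visit, record that the rating was unmasked and report it as a limitation.

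The cost is protocol wording, a short addition to the rating form and scheduling constraints. The documents already distinguish research assistants (III.2) from the clinicians who deliver treatment (V.2), but they give neither staff numbers nor who is trained to rate HARS, so capacity has to be confirmed. Some unmasking will still occur, and participants' own expectation effects remain. The sample size and power statement do not change.

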The hypothesis that I-CBT will yield greater reduction in opioid use and anxiety symptoms will be tested using separate linear mixed effects models for opioid use (weeks of use in the previous 4 weeks) and anxiety (HARS score) examining the main effect of treatment condition and its interaction with time on each outcome. The correlation among the repeated measures of the dependent variable will be appropriately accounted for via the inclusion of random subject effects (e.g., random intercepts and slopes for time). Covariates will include pre-treatment values of the dependent variable and any baseline demographic or clinical variables identified as necessary covariates in preliminary analyses.

To test the hypothesis that baseline stress reactivity is associated with treatment outcome at post-treatment (week 12), linear regressions will be utilized with primary opioid and anxiety outcomes at week 12 as the dependent variables and post-stress task anxiety, craving, and heart rate variability as independent variables, co-varying for baseline severity and any other covariates identified in preliminary analyses. In addition, to test the hypothesis that reduction in stress reactivity over time will be greater in the I-CBT condition, a linear mixed effects model will be conducted examining whether stress reactivity decreased from pre- to post-treatment and whether groups differed with respect to this change; this analysis will include the main effects of time and group and the time x group interaction. The correlation among repeated measures of the dependent variable will be accounted for via the inclusion of random subject effects.

With repeated assessments over 7 months of study participation, some amount of missing data is inevitable. Extensive efforts will be made throughout all stages of follow-up to minimize missing data by vigorous outreach, including to any participants who elect to dropout of treatment prior to completion. For all of the proposed analyses, we will use statistical methods (e.g., linear

mixed effects models) that incorporate partially observed data on participants who are lost to follow-up.

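### Stress-script order is randomised but left out of both Aim 3 analyses: this costs precision in Aim 3(b) if order is redrawn, and mildly attenuates the Aim 3(a) slopes

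*Combined protocol and SAP*

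**What the plan says.** Section V.4.3 (Stress Reactivity Assessment) describes the task: "The stress reactivity paradigm includes two imagery conditions (neutral-relaxing, stress related) and a laboratory session". On timing it says "This paradigm will be completed at pre- and post-treatment assessments", and on sequence "The order of the scripts will be randomized". It does not say whether a participant keeps one order at both sessions or gets a new draw. It gives no interval or return-to-baseline check between scripts. It does provide measurements around each script: "Psychophysiological measures (skin conductance) will be collected before, during, and after each imagery script", and "Subjective measures that will be administered prior to and following each imagery condition include the Positive and Negative Affect Scale", together with craving.

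Specific Aim 3(b) in section II predicts that "reductions in stress reactivity from baseline to post-treatment will be greater in the ICBT group relative to the IDC group". Section VI tests this with a linear mixed model with random subject effects, and "this analysis will include the main effects of time and group and the time x group interaction". For Aim 3(a), section VI regresses week-12 opioid and anxiety outcomes on values taken after the stress task (anxiety, craving and heart rate variability), adjusting for baseline severity and any covariates found in preliminary analyses. Script order appears in neither analysis. Section VI does not say how reactivity is scored for Aim 3(b).

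**The concern.** A stress script heard first is met from rest; heard second, it follows a relaxing script. If the first script still affects the response to the second, the measured response depends partly on order. The investigators set this factor themselves, so its effect can be removed by modelling it. Left out, it goes into the error.

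For Aim 3(b), a participant who switches order between sessions can show a change that is partly order. That widens the interval around the group difference in change, and section VI says the trial's focus is on estimating effect sizes and their reliability. For Aim 3(a), only the baseline session supplies the predictors, so an order effect cannot cancel within a person. It acts as measurement error in the predictor and pulls the slope toward zero.

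**Working it through.** **Inputs from the documents.** 54 participants (section III); two sessions and two scripts per session (section V.4.3); r = 0.42 for repeated HARS scores and r below 0.20 for opioid use (section VI).

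**Assumptions.** 1:1 allocation, so 27 per arm (no ratio is stated); two-sided alpha of 0.05 (not stated); r = 0.42 carried over to stress reactivity (no value is given for it); an additive order effect of δ = 0.3, 0.5 or 0.8 SD on the post-stress response (no value is given); each order equally likely; no losses.

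**The plan's own figure.** Section VI gives a detectable difference of d = .70-.75 at power 0.80 for Aim 2. With baseline adjustment, d = (1.96 + 0.84) x sqrt(1 - r²) x sqrt(2/27). This is 0.69 at r = 0.42 and 0.75 at r = 0.20, so the figure reproduces at the full 54. Aim 3 has only a verbal statement of detectable effect, and this point disputes no stated number.

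**Aim 3(b), bias.** Arm and order are assigned independently at random, so an order effect common to both arms has the same expected contribution in each and drops out of the difference in change. In simulation (40,000 trials per setting, 27 per arm, no true effect) the mean contrast was within 0.003 SD of zero and type I error was 0.050 to 0.052, whether order was kept or redrawn.

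**Aim 3(b), precision, order redrawn.** The order contribution to a participant's change is -δ, 0 or +δ with probabilities 0.25, 0.5 and 0.25, so its variance is δ²/2. Without order effects the change has variance 2(1 - 0.42) = 1.16. Power is for a between-arm difference in change of 0.84 SD, which has power 0.80 when δ = 0.

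| δ (SD) | δ²/2 | Increase over 1.16 | Simulated power |
|---|---|---|---|
| 0 | 0 | 0% | 0.80 |
| 0.3 | 0.045 | 4% | 0.79 |
| 0.5 | 0.125 | 11% | 0.76 |
| 0.8 | 0.320 | 28% | 0.70 |

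**Aim 3(b), order kept.** The same δ enters both sessions and cancels in the change. Simulated power stayed at 0.80 for every δ.

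**Chance imbalance between arms.** With redrawn order, the arm contrast moves by chance with SD δ x sqrt(0.5 x 2/27) = 0.19δ. This is the same loss seen from another side: (δ²/2) x (2/27) is exactly the variance already added in the table. It is not a second harm.

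**Aim 3(a).** With half the sample in each order, order adds δ²/4 to the variance of the predictor. Taking unit residual variance and a single predictor, the slope is multiplied by 1/(1 + δ²/4).

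- δ = 0.3: 0.0225/1.0225 = 2% attenuation
- δ = 0.5: 0.0625/1.0625 = 6%
- δ = 0.8: 0.16/1.16 = 14%

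This holds whether order is later kept or redrawn, because only the baseline session is used.

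**The case against.** A reader might infer that carry-over between scripts contaminates the Aim 3(b) test and could produce a false group difference. The documents do not support that. Aim 3(b) is a contrast between arms, and section IV states "Participants will be randomly assigned to receive either ICBT or IDC". Common carry-over adds noise, which the ordinary standard error already covers. Carry-over could distort the contrast only by differing between arms. For example, suppose reactivity is scored as stress minus neutral and a share L of the stress response spills into a neutral script that follows. Half the sample is affected, so a true effect shrinks by about L/2 (15% at an assumed L of 0.3). That dilutes an effect and does not create one.

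A reader might also infer that there is no recovery between scripts. The text is only silent on the interval, and several measurements fall between the two scripts.

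The strongest remaining objection is that each script has its own pre-script values, so a before-to-after score would remove part of any carry-over. That stands as far as it goes. But section VI does not say such a score is used: for Aim 3(a) it names post-task values, and for Aim 3(b) it gives no scoring rule. It is also fair that the Aim 3(b) loss depends on order being redrawn, which is not stated, and that it is slight at δ = 0.3. Finally, the open-ended covariate clause could admit order, but section VI directs it at baseline demographic and clinical variables, so order would not reliably enter by that route.

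**Conclusion.** The point holds as a minor one. A factor that the trial itself randomises is missing from both Aim 3 models. In Aim 3(b) this causes no bias when carry-over is equal in both arms. It costs precision if order is redrawn (power 0.80 to between 0.79 and 0.70 over the assumed range) and, for an additive effect, nothing if order is kept. In Aim 3(a) it attenuates the slopes by about 2% to 14% over the same range, whichever rule applies after treatment.

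All these sizes rest on an order effect the documents do not give, on a correlation borrowed from the HARS, and on 27 per arm with no losses. The Aim 3(a) figures also assume unit residual variance and one predictor. With less residual variance left after adjustment, attenuation would be larger.

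**What to change.** **Section VI.** Add script order at that session (stress first or second) as a fixed effect in the Aim 3(b) mixed model and as a covariate in the Aim 3(a) regressions, using the randomised order. For sessions already run this needs the order to have been kept on record, which the documents do not mention either way.

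**Section V.4.3.** For sessions not yet run, state that one order is drawn per participant and reused after treatment. The order term then adds little to Aim 3(b), because order is constant within a person, but it is still needed for Aim 3(a). It would also help to state the interval between scripts and how reactivity is scored.

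**Cost.** One line in the laboratory procedure and one degree of freedom per model, with no extra visits or data. If the order effect is small, so is the gain.
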